B.5 DATA MANAGEMENT	35
B.6 DOCUMENT RETENTION	35
B.7 DEVIATIONS	36
B.8 DEVICE ACCOUNTABILITY	36

B.9 DEVICE FAILURES AND PRODUCT NONCONFORMITIES.....	36
B.10 LIST OF INVESTIGATOR RESPONSIBILITIES	37
B.11 CONFIDENTIALITY	38
B.12 MONITORING	38
B.13 ENROLLMENT CONTROLS	39
B.14 SUSPENSION OR TERMINATION	39
B.15 PUBLICATION POLICY.....	40
APPENDIX C: STATISTICS AND DIAGNOSTIC ACURACY MEASURES.....	41
C.1 META-ANALYSIS OF NINE REFERENCES.....	41
C.2 SAMPLE SIZE CALCULATION	41
C.3 DIAGNOSTIC ACCURACY MEASURES	43

Protocol Synopsis

Full Title	A Multicenter, Prospective, Randomized Study on Endosonographic Evaluation of Pancreatic Cystic Lesions Using 22 G, 19 G, and Flexible 19 G Fine Needle Aspiration
Short Title	Randomized Evaluation of PCLs Using Three EUS-FNA Needles
Primary Objective	To document impact of EUS-FNA needle gauge and flexibility on effectiveness of pancreatic cystic lesions (PCL) aspiration, on ability to obtain sufficient material for standard diagnostic testing, and on diagnostic accuracy of EUS-FNA aspirate for differentiation of mucinous (pre-malignant) and non-mucinous cysts.
Devices	
Name Expect™ Endoscopic Ultrasound Aspiration Needle
 
Cleared Indication The Expect™ Needle is designed to sample targeted sub mucosal and extramural gastrointestinal lesions through the accessory channel of a curvilinear echoendoscope.
 
Device Categories
 
 • Expect 22 gauge (22 G) • Expect 19 gauge (19 G) • Expect 19 gauge Flex (19 G Flex)
Study Design	
Prospective, multi-center study
 
Three arm randomized (19 G Flex, 22 G, 19 G) in 2:1:1 ratio with salvage. Salvage procedure will use 19 G Flex for patients originally randomized to 19 G or 22 G standard needles, and will use 19 G or 22 G standard needle at investigator discretion for patients originally randomized to 19 G Flex needle.
 
Phased
 
 • Phase I: 2 centers • Phase II: expanded to 7 to 12 centers
Number of Subjects	250 patients (121 in 19 G Flex arm, and 61 patients each in 22 G and 19G arm, rounded up)
Number of Centers	7 to 12 centers
Primary	Volume of aspirated cyst fluid as a function of estimated maximal volume

Endpoint	based on pre-aspiration EUS measure of cyst diameter (s) (% aspiration of total estimated volume)
Secondary Endpoints	
Safety Endpoint
 
a. Occurrence, severity and relatedness of adverse events to the needle and procedure
 
Other Endpoints
 
b. Extent of cyst aspiration as measured by reduction of maximal cyst diameter before and after FNA (converted to volume by standard geometric formulation)
 
c. Successful echoendoscopic fine needle aspiration of PCL, defined as complete cyst aspiration or collection of aspirate adequate to perform two standard assays: cytology and carcinoembryonic antigen (CEA)
 
d. Ability to reach and penetrate the PCL, stratified by route of access and PCL location
 
e. Number of EUS-FNA needles and EUS-FNA needle passes used
 
f. Time needed for aspiration for each pass and time from first needle pass in to last needle pass out
 
g. Ease of needle passage in and out of echoendoscope and quality of needle visualization inside the cyst, categorized as Excellent, Very Good, Good, Fair, and Poor
 
h. Accuracy of two EUS-FNA-based standard assays (cytology and CEA) as a diagnostic measure of disease state categorized as one of the following: serous cyst, mucinous cyst, intra papillary mucinous neoplasm (IPMN), or pseudocyst
 
i. Post EUS-FNA patient management plan (clinical and/or imaging surveillance, percutaneous aspiration, surgical removal)
 
j. Impact of EUS-FNA based assays on diagnosis
 
k. Rate of cross-over to salvage arm

Follow-up Schedule	
 Baseline: Screening, Enrollment, Randomization, Demographics, Medical History, Lesion Location Procedure: Lesion Characteristics, EUS-FNA Procedure Details (including needle use and times), Aspirate Characteristics, Salvage Procedure (if needed), Adverse Events assessment (through discharge or approximately 2hrs post-procedure) 30-Day Follow-up: Adverse events, End of Study Long Term Clinical Follow-Up Chart Review: Assess patient

	status, Chart Review Details, Morphological Status, Cytopathological Status, Biochemical Status, Surgical Pathology
Inclusion Criteria	
 1. Pancreatic cystic lesion measuring 13mm or greater in largest diameter. 2. Indicated for EUS evaluation of the PCL including EUS-FNA. 3. Age 18 years of age or older. 4. Willing and able to comply with the study procedures and provide written informed consent form to participate in the study.
Exclusion Criteria	
 1. Cysts in which FNA is not indicated based on review by the clinician, including potential concern of blood vessel location relative to the cyst. 2. Requirement for anticoagulation using clopidogril, warfarin, or other long acting antiplatelet agents (with the exception of aspirin) that cannot be safely stopped according to institutional guidelines. 3. Standard contraindications for EUS. 4. Known pancreatic pseudocyst. 5. Pregnancy.
Statistical Methods and Sample Size	
The sample size of this study was computed based on the following assumptions on the primary endpoint, as well as for the secondary endpoint c):
 
Primary endpoint considerations:
 
 • The volume of actual aspirated cyst fluid as a function of estimated maximal volume either in 19 G or 19 G Flex Arm is superior by at least 10% compared to the 22 G Arm, detected with 90% conjunctive power, using multiple comparison Hochberg's step up method. • Requires 50 patients in 19 G Flex Arm, and 25 patients each in 22 G and 19 G Arms. 
Secondary endpoint c) considerations:
 
 • Superiority of EUS-FNA success rate in 19 G Flex Arm by 16% or more compared to both the success rate of the 19 G Arm and the 22 G Arm, detected with 80% conjunctive power, using multiple comparison Hochberg's step up method. • Requires 121 patients in 19 G Flex Arm, and 61 patients each in 22 G and 19G Arm, rounded up

	
The final sample size was considered to be the maximum of required sample sizes of the above stated two endpoints to make sure that the both endpoints are properly powered, namely 250 patients.

--	--

1. Introduction

Endoscopic ultrasound fine needle aspiration (EUS-FNA) has become the reference standard for preoperative diagnosis of pancreatic cystic lesions (PCLs).^{1,2} Limitations of EUS-FNA persist however and include poor cytological yield, modest sensitivity to detection of malignancy of neoplastic cysts, and incomplete aspiration of cyst fluid which limits the ability to perform tumor marker and cytological testing. Additionally, EUS-FNA may increase the risk of infectious complications compared to EUS without FNA. Adverse events may include but are not limited to pancreatitis, infection, and bleeding.^{2,3} Overall, however, EUS-FNA is considered a safe and effective procedure.

 - A retrospective Long Term Clinical Follow-Up Chart Review will be performed to collect up to 24 months of standard of care clinical information (if applicable).

A flow chart illustrating the study design is provided in **Figure 1** below.

Figure 1 – Study Design Flow Chart

4. Endpoints

4.1. Primary Endpoint

Volume of aspirated cyst fluid as a function of estimated maximal volume based on pre-aspiration EUS measure of cyst diameter (s) (% aspiration of total estimated volume).

4.2. Secondary Endpoints

Safety Endpoint

- Occurrence, severity and relatedness of adverse events to the needle and procedure.

Other Endpoints

- b. Extent of cyst aspiration as measured by reduction of maximal cyst diameter before and after FNA (converted to volume by standard geometric formulation).
- c. Successful echoendoscopic fine needle aspiration of PCL, defined as complete cyst aspiration or collection of aspirate adequate to perform two standard assays: cytology and carcinoembryonic antigen (CEA).

NOTES: Endpoint c) success is defined as:

- complete aspiration, defined as reaching a final cyst maximal diameter of less than 5mm attained with a maximum of 3 needle passes; in the case of a multilocular cyst, complete aspiration of the largest locule is required,

or

- collection of aspirate adequate to perform two standard assays: cytology and CEA, attained with a maximum of 3 needle passes

Total aspirate volume should be 3cc or more. In cases where less than 3cc of aspirate is obtained but cytology and CEA assays can be adequately completed, the primary endpoint is considered to have been met. Aspirate handling procedures are provided in Section 7.4 below.

- d. Ability to reach and penetrate the PCL, stratified by route of access and PCL location.
- e. Number of EUS-FNA needles and EUS-FNA needle passes* used.
- f. Time needed for aspiration for each pass and time from first needle pass in[†] to last needle pass out[‡].

DEFINITIONS:

**Needle pass* -- from needle insertion through needle removal outside the cyst lumen, but not including needle repositioning within a single or multi-compartment cyst.

Note: A maximum of 3 needle passes are allowed, after which the EUS-FNA procedure will be considered failed.

[†]*Time of first needle pass in* -- time of the first needle puncture into the cyst lumen.

[‡]*Time of last needle pass out* -- time of removal of needle outside the cyst lumen at the end of the last fluid aspiration from a single or multi-loculated cyst, or after 10 seconds of failed attempt to aspirate fluid after the last needle re-positioning in a single or multi-compartment cyst.

- g. Ease of needle passage in and out of echoendoscope and quality of needle visualization inside the cyst, categorized as *Excellent, Very Good, Good, Fair, and Poor*.
- h. Accuracy of two EUS-FNA-based standard assays (cytology and CEA) as a diagnostic measure of disease state categorized as one of the following: *serous cyst, mucinous cyst, intra papillary mucinous neoplasm (IPMN), or pseudocyst*.

NOTES:

- Determination of disease state per EUS-FNA will be based on results from cytology and CEA and will follow published criteria.⁴ Definitions of the diagnostic accuracy measures are provided in **Appendix C.3**.
- Samples that do not have both diagnostic assay results (cytology and CEA) will be labeled as *Indeterminate*.

- i. Post EUS-FNA patient management plan (clinical and/or imaging surveillance, percutaneous aspiration, surgical removal).
- j. Impact of EUS-FNA based assays on diagnosis.
- k. Rate of cross-over to salvage.

5. Subject Selection

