8.3. Procedure

8.3.1. Lesion Characteristics

The following lesion characteristics will be assessed by EUS prior to the start of the FNA procedure and will be recorded on the *Procedure CRF*:

- a. Cyst size (maximal diameter, and cross-sectional diameter)

NOTE: In the case of a multilocular cyst, size will be measured both as the aggregate size of all cyst locules and the long and short perpendicular axis of the largest locule.

- b. Number of locules (1, 2, 3, 4, 5, 6-10, > 10)
- c. Presence of visible mucin (floating, or mobile filling defects)
- d. Presence of mural nodule (non-mobile filling defect) and size
- e. Presence of solid components
- f. Presence of distinct PCL wall
- g. Connectivity to pancreatic duct
- h. Maximal pancreatic duct diameter

An EUS image of the patient's PCL will be saved during the procedure.

8.3.2. *EUS-FNA Procedure*

The EUS-FNA procedure will be carried out in line with the guidelines provided in **Section 7** above, and the following data will be collected and recorded on the *Procedure CRF*:

- a. Route of access (gastric, duodenal, esophageal)
- b. Ease of insertion of EUS-FNA needle through echoendoscope
- c. Ability to reach target lesion
- d. Ability to penetrate into target lesion
- e. Quality of needle visualization
- f. Number of needle passes
- g. Ease of removal of EUS-FNA needle from echoendoscope
- h. Aspirate characteristics and adequacy of aspirate volume to perform two assays (cytology and CEA)
- i. Adverse Event assessment during procedure and through 2 Hours Post-Procedure or discharge from endoscopy unit

8.4. **Cytology and Chemistry Results**

The results of cyst aspirate cytology and CEA assessments will be provided by the cytology and chemistry labs and will be recorded on the *Cytology and Chemistry Results CRF*. Results will be categorized as follows⁴ and will be used for determination of Disease State per EUS-FNA:

- Cytology
 - Bland PAS +
 - Mucinous
 - Pigmented histiocytes
- CEA (ng/mL)
 - < 0.5
 - > 0.5 and < 200
 - > 200

8.5. **30-Day Follow-up**

The post-procedure 30-day Follow-up Visit will be conducted over the telephone. The visit window allows for this visit to occur anytime from 25 days to 35 days post procedure. Patients will be assessed for potential adverse events that might have occurred from discharge until 30 days post-procedure. AE information will be recorded on the *Adverse Event CRF*.

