12 AUG 2016

FINAL

Boston Scientific

Randomized Evaluation of PCLs Using Three EUS-FNA Needles

90869947 Rev/Ver. AG

Page 41 of 46

Design Parameters:

One-sided Type I Error=0.05

Multiple comparison procedure= Hochberg's step up

Total Sample required=100

Rejection region=Right tail

Treatment parameters:

Arm	Mean volume ratio	Standard Deviation	Sample size per group
22G	67	15.29	25
19G	77	4.67	25
19GFlex	77	4.67	50

Overall:

Global (reject any H_i): 0.912

Conjunctive (reject all H_i): 0.901

Secondary endpoint c) considerations:

It is the desire of this study to demonstrate superiority of the EUS-FNA 19 G Flex needle over two other needles:

- One offering the same needle diameter, but without added needle flexibility, namely the standard 19 G needle
- One offering better needle flexibility via a reduced needle diameter, namely the standard 22 G needle

Superiority by 16% or more is deemed clinically significant. Statistical power of 80% is chosen using the multiple comparison Hochberg's method. Test results are shown below, resulting in the requirement for 121 patients for 19 G Flex arm and 61 patients each for 19 G and 22G arm.

Hypothesis:

$H_i: \pi_i - \pi_0 \leq 0$ Versus $K_i: \pi_i - \pi_0 >$ for $i=1,2$

Design Parameters:

One-sided Type I Error=0.05

Multiple comparison procedure= Hochberg's step up

Total Sample required=243

Rejection region=Right tail

Treatment Parameters:

Arm	Response rate	Sample size per group
19GFlex	0.91	121
19G	0.75	61
22G	0.75	61

Overall:

Global (reject any H_i): 0.947

Conjunctive (reject all H_i): 0.808

C.3 Diagnostic Accuracy Measures

Diagnostic accuracy is defined in terms of “disease state” and the following three disease state categories will be used in this study in order to assess diagnostic accuracy of EUS-FNA:

- “*Disease State per EUS-FNA*”: This measure is derived from the results of the cytology and chemistry assays of the cyst aspirate. Cysts will be classified as *serous cyst*, *mucinous cyst*, *IPMN*, or *pseudocyst* based on the table below.⁴ If any of the aspirate assays are not performed or the results from the two aspirate-based assays do not follow the table below, then the Disease State per EUS-FNA will be classified as *Indeterminate*. The Disease State per EUS-FNA will be recorded on the *Cytology and Chemistry Results CRF*.

Disease State per EUS-FNA	Cytology	Cyst Fluid CEA (ng/mL)
Serous	Bland PAS +*	< 0.5
Mucinous	Mucinous	> 200
IPMN	Mucinous	> 200

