Pseudocyst	Pigmented histiocytes	< 200

* This cytological assay might be replaced by another cytological assay as needed

In order to assess the accuracy of EUS-FNA-based standard assays (cytology and CEA) as a diagnostic measure of disease state, the *Disease State per EUS-FNA* measure will be compared to a reference diagnosis. The reference diagnostic standard will be diagnosis from a surgical specimen histology, the true gold standard for cases that evolve to surgical resection within the 30 day follow-up time of the protocol. For cases that do not progress to surgery within 30 days of the EUS-FNA procedure, the reference diagnostic standard will be a composite diagnosis by a consensus board. The consensus board will consist of 3 to 5 Investigators who will be blinded to the type of needle used. The diagnosis of disease state

will be based solely on baseline medical history and EUS and cross sectional imaging of the cyst. Information regarding aspirate characteristics and results from aspirate tests will not be provided to the consensus board. Diagnoses will be rendered at a separate Investigators Meeting or virtual meeting.

- “*Disease State per Histology*”: This is the reference diagnostic standard. This measure is derived from the histology results of the surgical specimen in cases that progress to surgery within 30 days. Cysts will be classified as follows: *serous cyst*, *mucinous cyst*, *IPMN*, *pseudocyst*, or *Indeterminate*. As described above, this measure will serve as the gold standard for assessing diagnostic accuracy.
- “*Disease State per Consensus Board*”: This is the surrogate for the reference diagnostic standard. This measure is derived by the consensus board as described above. Cysts will be classified as follows: *serous cyst*, *mucinous cyst*, *IPMN*, *pseudocyst*, or *Indeterminate*. The classification will be based on baseline medical history and EUS and cross sectional imaging. Medical history will include, but not be limited to presence or absence of prior necrotizing pancreatitis, trauma or other potential cause of pseudocyst. Imaging will pertain to cyst location and cyst appearance.

Degree of correlation between *Disease State per EUS-FNA* and *Disease State per Consensus Board or per Histology* is illustrated below.

Total number of patients enrolled is sum of all entries, namely

$$\text{TOTAL} = A + B + C + \dots + S + T + U + V + W + X + Y.$$

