PCL Type	Serous per Consensus Board or Histology	Mucinous per Consensus Board or Histology	IPMN per Consensus Board or Histology	Pseudocyst Per Consensus Board or Histology	Indeterminate per Consensus Board or Histology
Serous per EUS-FNA	A	E	F	G	U
Mucinous per EUS-FNA	K	B	H	I	V
IPMN per EUS-FNA	L	M	C	J	W
Pseudocyst Per EUS-FNA	N	O	P	D	X
Indeterminate Per EUS-FNA	Q	R	S	T	Y

Degree of correlation between *Disease State per EUS-FNA* and *Disease State per Consensus Board or per Histology*:

- $[A+B+C+D+Y] / [TOTAL]$

Diagnostic accuracy for Serous Cysts:

- Sensitivity
 $= [A] / [A+K+L+N+Q]$
- Specificity
 $= [B+C+D+H+I+J+M+O+P+R+S+T+V+W+X+Y] / [B+C+D+E+F+G+H+I+J+M+O+P+R+S+T+U+V+W+X+Y]$
- Positive Predictive Value (PPV)
 $= [A] / [A+E+F+G+U]$
- Negative Predictive Value (NPV)
 $= [B+C+D+H+I+J+M+O+P+R+S+T+V+W+X+Y] / [B+C+D+H+I+J+K+L+M+N+O+P+Q+R+S+T+V+W+X+Y]$
- Overall Accuracy
 $= [A+ B+C+D+H+I+J+M+O+P+R+S+T+V+W+X+Y] / [TOTAL]$

Diagnostic accuracy for Mucinous Cysts:

- Sensitivity
 $= [B] / [B+M+O+E+R]$
- Specificity
 $= [A+C+D+Y+F+G+J+L+N+P+Q+S+T+U+W+X] / [A+C+D+F+G+H+I+J+K+L+N+P+Q+S+T+U+W+X+Y+V]$
- Positive Predictive Value (PPV)
 $= [B] / [B+H+I+K+V]$
- Negative Predictive Value (NPV)
 $= [A+C+D+F+G+J+L+N+P+Q+S+T+Y+U+W+X] / [A+C+D+E+F+G+J+L+M+N+O+P+Q+R+S+T+U+W+X+Y]$
- Overall Accuracy
 $= [A+B+C+D+F+G+J+L+N+P+Q+S+T+U+W+X+Y] / TOTAL$

Diagnostic accuracy for IPMN:

- Sensitivity
 $= [C] / [C+F+H+P+S]$
- Specificity

$$= [A+B+D+E+G+I+K+N+O+Q+R+T+U+V+X+Y] / [A+B+D+E+G+I+J+K+L+M+N+O+Q+R+T+U+V+X+Y+W]$$

- Positive Predictive Value (PPV)
 $= [C] / [C+J+L+M+W]$
- Negative Predictive Value (NPV)
 $= [A+B+D+E+G+I+K+N+O+Q+R+T+U+V+X+Y] / [A+B+D+E+F+G+H+I+K+N+O+P+Q+R+S+T+U+V+X+Y]$
- Overall Accuracy
 $= [A+B+C+D+E+G+I+K+N+O+Q+R+T+U+V+X+Y] / \text{TOTAL}$

Diagnostic accuracy for Pseudocysts (in principle excluded from study, but a few cases may not have been identified at baseline as such):

- Sensitivity
 $= [D] / [D+G+I+J+T]$
- Specificity
 $= [A+B+C+E+F+H+K+L+M+Q+R+S+U+V+W+Y] / [A+B+C+E+F+H+K+L+M+N+O+P+Q+R+S+U+V+W+Y+X]$
- Positive Predictive Value (PPV)
 $= [D] / [D+N+O+P+X]$
- Negative Predictive Value (NPV)
 $= [A+B+C+E+F+H+K+L+M+Q+R+S+U+V+W+Y] / [A+B+C+E+F+G+H+I+J+K+L+M+Q+R+S+T+U+V+W+Y+X]$
- Overall Accuracy
 $= [A+B+C+D+E+F+H+K+L+M+Q+R+S+U+V+W+Y] / \text{TOTAL}$

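### Endpoint h's agreement measure scores Indeterminate by EUS-FNA with Indeterminate by reference as agreement, and the closed reference list sends definite diagnoses outside four types to Indeterminate

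*Protocol*

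**What the plan says.** Endpoint h (Protocol 4.2; SAP 5.1.1) concerns disease state "categorized as one of the following: *serous cyst, mucinous cyst, intra papillary mucinous neoplasm (IPMN), or pseudocyst".

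**EUS-FNA side.** Protocol 8.4 provides three cytology categories: bland PAS+, mucinous and "Pigmented histiocytes". None is for malignant cells. Two rules lead to Indeterminate. The notes to endpoint h state: "Samples that do not have both diagnostic assay results (cytology and CEA) will be labeled as *Indeterminate". Appendix C.3 applies the same label in wider circumstances: "If any of the aspirate assays are not performed or the results from the two aspirate-based assays do not follow the table below".

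**Reference side.** The reference is surgical histology if resection occurs within 30 days, and otherwise a consensus board. For each, Appendix C.3 says: "Cysts will be classified as follows: *serous cyst*, *mucinous cyst*, *IPMN*, *pseudocyst*, or *Indeterminate". No other class is offered, and there is no rule for a definite diagnosis outside the list.

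**Agreement.** The 5 × 5 table in Appendix C.3 (repeated in SAP 5.1.2) has a last row "Indeterminate Per EUS-FNA" and a last column "Indeterminate per Consensus Board or Histology". They meet in cell Y. Both documents define the degree of correlation as [A+B+C+D+Y]/TOTAL, where TOTAL is all enrolled patients.

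**The concern.** An agreement rate should credit the test when it names the right diagnosis. In cell Y the test named none, often because an assay was not done, and the reference named none of the four classes either. The two labels do not mean the same thing: one records a missing or off-table laboratory result, the other an unclassified lesion. Their coincidence is not a correct result.

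The closed reference list adds patients to that column. Eligibility admits any cyst of 13 mm or more with FNA indicated, and known pseudocyst is the only cyst type excluded by name. A lesion that histology identifies as something outside the four types therefore has a firm diagnosis but can only be coded Indeterminate. A failed aspirate in that patient then counts as agreement, while an aspirate read as one of the four classes counts as disagreement.

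The comparison of needles is at stake. Diagnostic accuracy of the aspirate is part of the stated primary objective (Protocol 2), and results are to be shown by randomised needle (Protocol 9.3; SAP 4.1). Needles may differ in how often they give usable fluid, so a measure that credits unusable fluid blurs the contrast the trial was set up to describe.

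**Working it through.** Neither document states an expected accuracy, power or sample size for endpoint h, so there is no figure to reproduce. The check rebuilds the table and works out what Y contributes.

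**Step 1: the table.** Rows are EUS-FNA, columns are the reference, in the order serous, mucinous, IPMN, pseudocyst, Indeterminate:

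| EUS-FNA row | Ser | Muc | IPMN | Pseu | Indet |
|---|---|---|---|---|---|
| Serous | A | E | F | G | U |
| Mucinous | K | B | H | I | V |
| IPMN | L | M | C | J | W |
| Pseudocyst | N | O | P | D | X |
| Indeterminate | Q | R | S | T | Y |

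The diagonal is exactly A, B, C, D, Y, which is the printed numerator. In the last column only Y scores as agreement; U, V, W and X score as disagreement. Within that column the agreement rate therefore equals the share of FNA results that are Indeterminate, and rises with it.

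**Step 2: inflation.** Let r be the share of patients with an Indeterminate reference and f the share with an Indeterminate FNA result, taken as independent. The documents give neither, so both are assumptions. Y/TOTAL = r × f.

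- r = 5%, f = 30%: 0.05 × 0.30 = 1.5 points (3.75 of 250 patients).
- r = 15%, f = 60%: 0.15 × 0.60 = 9.0 points (22.5 of 250).
- With lower assumptions, r = 2-10% and f = 10-60%: 0.02 × 0.10 = 0.2 points up to 0.10 × 0.60 = 6.0 points.

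**Step 3: difference between arms.** Let a be the proportion correct among cysts given a named class on both sides, assumed to be 80%. Agreement without Y is (1 − r)(1 − f)a; with Y it is (1 − r)(1 − f)a + rf. Compare a needle with f = 30% and one with f = 60%:

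| r | Measure | f = 30% | f = 60% | Gap (points) |
|---|---|---|---|---|
| 5% | without Y | 0.95 × 0.70 × 0.80 = 53.2% | 0.95 × 0.40 × 0.80 = 30.4% | 22.8 |
| 5% | with Y | 53.2 + 1.5 = 54.7% | 30.4 + 3.0 = 33.4% | 21.3 |
| 15% | without Y | 0.85 × 0.70 × 0.80 = 47.6% | 0.85 × 0.40 × 0.80 = 27.2% | 20.4 |
| 15% | with Y | 47.6 + 4.5 = 52.1% | 27.2 + 9.0 = 36.2% | 15.9 |

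The gap shrinks by 1.5 points (22.8 − 21.3) or 4.5 points (20.4 − 15.9).

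**Step 4: could the sign reverse?** With Y counted, the change in agreement when f rises is (rise in f) × [r − (1 − r)a]. It is positive only if a < r/(1 − r), which is 0.05/0.95 = 5.3% at r = 5% and 0.15/0.85 = 17.6% at r = 15%.

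**The case against.** The strongest reply is that failed aspirates are already penalised. With a named reference class they fall in Q, R, S or T, which count as disagreement and sit in the sensitivity denominators. Y enters no sensitivity or PPV formula. Endpoint h is summarised descriptively, with no planned test. All of this stands, and it limits the size of the point. It does not make Y a correct diagnosis.

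It can also be said that Y is not all failure: an adequate sample whose results do not fit the cytology/CEA table lands there too. That is true, so Y mixes failure with possible concordance. That mixture is a reason to report it separately and not as agreement.

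Four stronger readings are tempting and are not supported.

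- **The needle with fewer usable aspirates comes out ahead.** Step 4 shows that this needs an accuracy below about 5-18% among classified cysts. At 80%, the worse needle still trails by 15.9-21.3 points.
- **Every proven cancer must be coded Indeterminate.** The list sorts cyst type, not grade. A cancer arising in an IPMN or mucinous cyst could be filed under its parent class, and no sentence prevents it. The elimination is firm only for types outside the four.
- **Definitive diagnoses are lost to the trial.** Surgical pathology and cytopathological status are collected by chart review for up to 24 months (Protocol 8.1 and 8.6). The diagnoses are missing from this table, not from the data.
- **The trial fails an aim of detecting malignancy.** The Introduction lists "modest sensitivity to detection of malignancy of neoplastic cysts" among several limitations of EUS-FNA, but the stated diagnostic aim is to separate mucinous from non-mucinous cysts.

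**Conclusion.** The agreement measure is wrong as written: it credits an absent FNA diagnosis as correct whenever the reference is Indeterminate. This follows from the printed formula and needs no assumption. The closed reference list enlarges that column by an amount the documents do not let one estimate. It may be small, since histology is the reference only after resection within 30 days, although the same list binds the consensus board.

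The sizes rest on assumed values. With r of 5-15% and f of 30-60%, independent, agreement is inflated by 1.5-9.0 points. That r covers every Indeterminate reference, including ordinary unresolved cases, so the figure is not the effect of the missing classes alone. With 80% accuracy and f of 60% against 30%, the arm difference falls from 22.8 to 21.3 points at r = 5% and from 20.4 to 15.9 at r = 15%. The effect is dilution, not reversal, in a descriptive secondary endpoint. The correction is cheap and should be made.

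**What to change.** In Protocol Appendix C.3 and SAP 5.1.2:

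1. Drop Y from the agreement numerator. Count agreement only where a named FNA class matches the same named reference class.
2. Report the number of Indeterminate FNA results by arm, separating assays not done from results that do not fit the table.
3. Add an 'other (specify)' reference class, for histology and for the consensus board, to hold definite diagnoses outside the four types. Keep reference Indeterminate for cases in which no diagnosis could be made.
4. State how a cancer arising in a mucinous cyst or IPMN is classed.
5. If a malignant cytology category is added to Protocol 8.4, add a matching row to the cytology/CEA table; otherwise such results still become Indeterminate. Update the per-class formulas for any added class.

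Items 1 and 2 need only a change to the text and the programs. Items 3 to 5 cost a form option or two, a wider table and revised formulas. The reported agreement will be slightly less favourable.
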